1.3.7 DOSE AND REGIMEN RATIONALE

The intent is to evaluate INO-4800 as a prophylactic vaccine against COVID-19 disease. Based on Inovio's extensive experience developing vaccine candidates against infectious diseases via the ID route ([54], [33]), a 2-dose regimen was considered to be optimal, based on the balanced humoral and cellular responses obtained 2 weeks post-dose 2, which supports evaluation of a 2-dose regimen (Days 0 and 28).

In the Phase 2 segment of this trial, 1.0 mg and 2.0 mg of vaccine were administered by ID injection and followed immediately by EP at Day 0 and Day 28. The selection of the doses to test in Phase 2 is supported by the safety profile in the Phase 1 trial of INO-4800 (COVID19-001, NCT04336410) in addition to our prior experience in developing a MERS coronavirus (MERS-CoV) vaccine (INO-4700) [16, 17]. The safety data for INO-4800 is provided in the Investigator's Brochure (IB).

The objective of the Phase 2 segment of the Phase 2/3 trial was to further evaluate the 1.0 mg and 2.0 mg doses of INO-4800 for each age group in order to select the optimal vaccination regimen in the Phase 3 efficacy segment. The final decision between the two doses by age group relies on safety and immunogenicity. The 1.0 mg and 2.0 mg doses in the Phase 1 study had a similar safety profile. The review of the Phase 2 data by the independent DSMB has not revealed any safety signals of concern to date. Furthermore, there have not been substantial differences in the safety profile between the 1.0 mg and 2.0 mg dosing groups to impact Phase 3 dose selection. However, the interim immunology data from the Phase 2 study revealed favorable immunogenicity with the 2.0 mg dose over the 1.0 mg dose. Data were analyzed for two age groups: ≥18 to ≤50 years of age and ≥51 years of age. The results illustrate that the 2.0 mg dose induced higher levels of SARS-CoV-2 spike specific antibodies as well as higher levels of IFN-gamma producing cells.

1.3.7.1 **Binding Antibody Response**

The binding antibody response was measured for all Phase 2 subjects at Day 0 and Week 6. Across all ages, the geometric mean titer (GMT) for the 1.0 mg dose group was 123.3 at Day 0 compared to 938.8 at Week 6. The geometric mean fold rise was 7.8. The GMT for the 2.0 mg dose group was 93.5 at baseline compared to 2210.0 at Week 6. The geometric mean fold rise was 23.5.

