3.0 CLINICAL TRIAL DESIGN AND ENDPOINTS

This is an operationally seamless Phase 2/3, randomized, placebo-controlled, multicenter trial to evaluate the safety, immunogenicity, and efficacy of INO-4800, administered by ID injection followed immediately by EP using the CELLECTRA[®] 2000 device, in a 2-dose regimen (Days 0 and 28) in adults who are at high risk of SARS-CoV-2 exposure. Subjects 18 years of age and older are expected to be enrolled across two (2) segments of this study. In the Phase 2 segment, approximately 400 seronegative subjects will be enrolled. In the Phase 3 segment, approximately 6714 seronegative subjects are expected to be enrolled, and 402 seropositive subjects will be enrolled. The subjects and data from Phase 2 are independent from that of Phase 3. The primary objectives of this trial are to identify in seronegative subjects an optimal age-related dose (Phase 2 segment) for subsequent evaluation for efficacy (Phase 3 segment).

Phase 2 Segment – Dose Selection

In the Phase 2 segment, approximately 400 subjects 18 years of age and older will be evaluated across four (4) dose groups (Table 1, Figure 1). Subjects will be randomized at a 3:3:1:1 ratio to receive either 1.0 mg or 2.0 mg of active investigational product (INO-4800) or 1 or 2 injections of placebo (placebo for INO-4800). Dose groups receiving INO-4800 will enroll approximately 150 subjects per group. Dose groups receiving placebo will enroll approximately 50 subjects per group. Randomization will be such that approximately 240 subjects aged 18-50 years, 120 subjects aged 51-64 years and 40 subjects aged \geq 65 years will be enrolled. Initial enrollment will include subjects aged 18-50 years. Initiation of enrollment of older subjects 51-64 years of age and elderly subjects 65 years and older will depend on review of safety and immunogenicity data from those age groups generated in the Phase 1 study (COVID19-001).

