This segment of the trial is case-driven. Among seronegative subjects, a total of 149 observed cases will be required for 90% power to declare the vaccine efficacious (>30%), assuming a true efficacy of 60%. A sample size of 6714 seronegative subjects is expected to be required to achieve the 149 cases assuming an underlying attack rate of 3.7%. The actual sample size may differ if the observed attack rate is different than projected. There are two formal interim analyses of efficacy; one when 50% of the cases accrue and one when 75% of the cases accrue. If the prespecified criteria for efficacy are met at either interim analysis, then enrollment will continue until 4500 subjects have been enrolled, and blinded follow-up will continue until at least those 4500 subjects have a minimum of 6 months of safety follow-up. At that point, the trial would be unblinded and placeborecipients will be offered the active product.

The primary efficacy endpoint window will begin 14 days post-dose 2 and will end at 12 months post-dose 2. All Phase 3 segment subjects will be followed for 56 weeks from the Day 0 dosing [i.e., Week 56 will be the planned End of Study (EOS) visit for this segment of the trial].

External Committee Reviews

For both the Phase 2 and 3 segments, the Data Safety Monitoring Board (DSMB) will convene regularly to review all available unblinded safety data, and additionally upon completion of the Week 8 phone call visit for all subjects enrolled during the Phase 2 segment. For the Phase 3 segment, the DSMB will also review efficacy in an unblinded fashion. Additionally, for Phase 3, an independent, blinded Endpoint Adjudication Committee (EAC) will review and confirm COVID-19 cases.

Details of each committee's scope will be provided in the respective charters.

3.1 **PRIMARY OBJECTIVES**

See Table 6.

3.2 **PRIMARY ENDPOINTS**

Table 6: Primary Objectives and Associated Endpoints

Phase 2 Primary Objective	Phase 2 Primary Endpoints
1. Evaluate the cellular and humoral immune response to INO-4800	1a. Antigen-specific cellular immune response measured by IFN-gamma ELISpot assay
administered by ID injection followed immediately by EP	1b. Neutralizing antibody response measured by a pseudovirus-based neutralization assay
Phase 3 Primary Objective	Phase 3 Associated Primary Endpoint

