Subjects who require medical care for COVID-19 (or any other suspected condition) will be referred to their primary health care provider or a medical treatment facility if the Investigator believes that the subject should be managed beyond routine care that can be provided by the study site. Subjects referred for treatment will continue study follow-up according to the protocol schedule. If subjects are treated or hospitalized due to their illness, the study team will request COVID-19 specific test results, treatments, treatment outcomes and diagnostics from medical treatment facilities with the subject's written permission. These results and diagnostics will be recorded in the study and/or safety database consistent with protocol reporting requirements.

6.5 **IMMUNOGENICITY ASSESSMENTS**

Whole blood and serum samples will be obtained at visits specified in the Schedule of Events (Tables 3 and 4) for cellular and humoral immunology assessments. Binding ELISA will be evaluated at serial timepoints. Cellular sampling requires 32 mL of whole blood be collected at each visit. Humoral sampling requires collection of 8.5 mL of whole blood in a single 10-mL red top serum collection tube to produce two serum aliquots of 2 mL each. However, baseline (Day 0) immunology samples are required to serve as a baseline for all subsequent immunology testing. Therefore, a total of 68 mL whole blood for cellular sampling and 8 mL serum for humoral sampling is required on Day 0 prior to 1st dose. Subjects may be asked to return for additional blood draws if collected blood sample is lost or unevaluable for any reason. Details of the immunology sample collection and shipment information will be provided in the Laboratory Manual.

Humoral samples will be collected on all subjects and cellular samples will be collected at selected sites (from approximately 711 subjects). Both humoral and cellular analysis will be conducted in the first 102 subjects age 18-50 and in the first 102 subjects age 51 and older enrolled at the sites that are selected for cellular sample collection. In addition, cellular and humoral samples will be analyzed on all subjects with COVID-19 when samples are available.

The immune responses to INO-4800 will be measured using assays that include a pseudovirus-based neutralization assay and ELISpot. Determination of additional analyses using assays not specified, such as assessment of immunological gene

Protocol Version: 2.0USA

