8.5.1 PRIMARY ANALYSIS

Phase 2 Segment

Post-baseline increases from baseline in interferon-γ ELISpot response magnitudes will be compared between treatment groups using differences in medians and associated non-parametric 95% CIs.

INO-4800	COVID19-311
Inovio Pharmaceuticals, Inc.	Clinical Protocol

Post-baseline increases from baseline in neutralizing antibody response titers will be compared between treatment groups using ratios of geometric mean fold-rises and associated t-distribution based 95% CIs.

The summaries listed above will be stratified according to NP positive/negative status and according to prior receipt of any non-study prophylactic COVID-19 vaccine of the subjects. Valid samples for statistical analysis purposes will be those collected: at least 6 and no more than 30 days after Dose 2 for the Week 6 timepoint; at least 174 and no more than 198 days after Dose 2 for the Week 30 timepoint; and at least 356 and no more than 380 days after Dose 2 for the Week 56 timepoint. Baseline is defined as the last measurement prior to the first treatment administration.

The PP population will be used for these immunogenicity analyses.

Phase 3 Segment

Among subjects who are SARS-CoV-2 seronegative at baseline, the primary hypothesis of relative efficacy greater than 30% will be tested with H_0 : $p \ge 0.70/(0.70+k)$ vs. H_1 : p < 0.70/(0.70+k), where p is the true proportion of subjects with disease who receive INO-4800 relative to the total number of subjects with disease, and k is the total amount of follow-up time in the placebo group divided by the total amount of follow-up time in the INO-4800 group.

A p-value for this hypothesis test and corresponding confidence interval will be computed based on the exact binomial method of Clopper-Pearson. Success will be concluded if the one-sided p-value is <0.022 and the corresponding lower bound of the two-sided 95.6% Cl for efficacy exceeds 30% (alpha-level adjusted for interim analyses, see Section 8.5.6), and the point estimate for efficacy exceeds 50%.

For calculating k, an individual subject's follow-up time is either:

- the date of first disease diagnosis date of the start of surveillance period +1 (for subjects who are cases), or
- the date of last follow-up date of the start of surveillance period +1 (for subjects who are non-cases).

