8.5.2.2 Immunogenicity

Phase 3 Segment

Post-baseline increases from baseline in interferon- γ ELISpot response magnitudes will be compared between treatment groups using differences in medians and associated non-parametric 95% CIs.

Post-baseline increases from baseline in neutralizing antibody response titers will be compared between treatment groups using ratios of geometric mean fold-rises and associated t-distribution based 95% CIs.

The summaries listed above will be stratified according to disease status of the subjects and by baseline SARS-CoV-2 serostatus.

Valid samples for statistical analysis purposes will be those collected: at least 6 and no more than 30 days after Dose 2 for the Week 6 timepoint; at least 174 and no more than 198 days after Dose 2 for the Week 30 timepoint; and at least 356 and no more than 380 days after Dose 2 for the Week 56 timepoint. Baseline is defined as the last measurement prior to the first treatment administration.

The PP population will be used for these immunogenicity analyses.

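### Section 8.5 fixes the immunogenicity strata without age, although the protocol frames the Phase 2 dose decision by age group and draws the Phase 3 assay subset by age

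*Protocol*

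**What the plan says.** On the aim, Section 3.0 states: "The primary objectives of this trial are to identify in seronegative subjects an optimal age-related dose (Phase 2 segment) for subsequent evaluation for efficacy". Section 1.3.7 adds: "The final decision between the two doses by age group relies on safety and immunogenicity". Phase 2 enrolment is set by age at about 240 (18-50), 120 (51-64) and 40 (65 and over).

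On the analysis, Section 8.1 says that the formal statistical analysis plan is what follows in Section 8. Within it:

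- Section 8.5.1, Phase 2 primary analysis: "The summaries listed above will be stratified according to NP positive/negative status and according to prior receipt of any non-study prophylactic COVID-19 vaccine". Section 8.5.9.2 uses the same two strata for the exploratory Phase 2 assays.
- Section 8.5.2.2, Phase 3: "The summaries listed above will be stratified according to disease status of the subjects and by baseline SARS-CoV-2 serostatus". Section 8.5.9.2 uses disease status alone for Phase 3.
- Section 8.5.3.1 splits the Phase 2 safety summaries by prior non-study vaccine only.

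Phase 3 randomisation is stratified at age 51 (Section 8.7). Section 6.5 runs both humoral and cellular assays "in the first 102 subjects age 18-50 and in the first 102 subjects age 51 and older" enrolled at the sites chosen for cellular sampling.

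On what has been done, Section 1.3.7 reports: "Data were analyzed for two age groups: ≥18 to ≤50 years of age and ≥51 years of age".

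**The concern.** The stated purpose and the written analysis do not match. The protocol sets age quotas in Phase 2, says the dose decision is made by age group, and stratifies both randomisation and the Phase 3 assay subset by age. The section that fixes the immunogenicity summaries then lists its strata by name and leaves age out.

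Section 8 declares itself the formal plan and lists the strata explicitly, so the omission cannot be put down to detail left for another document. Followed as written, each planned immunogenicity comparison is a contrast pooled over age within the listed strata. At stake is whether the reader gets an estimate with a confidence interval for each age group, on a cut chosen in advance, or only an age reading made outside the plan.

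**Working it through.** **1. The passages side by side.**

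| Element | Uses age? | Where |
|---|---|---|
| Phase 2 aim | yes | 3.0 |
| Basis of dose decision | yes | 1.3.7 |
| Phase 2 enrolment quotas | yes (three bands) | 3.0 |
| Week 6 interim reading | yes (two bands) | 1.3.7 |
| Phase 3 randomisation strata | yes (two bands) | 8.7 |
| Phase 3 assay subset | yes (two bands) | 6.5 |
| Phase 2 immunogenicity strata | no | 8.5.1, 8.5.9.2 |
| Phase 3 immunogenicity strata | no | 8.5.2.2, 8.5.9.2 |
| Phase 2 safety split | no | 8.5.3.1 |

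**2. Is there a genuine by-age reading behind 1.3.7?** The pooled geometric mean titre should be a weighted geometric mean of the two age groups. The implied weight of the 18-50 group is (ln pooled − ln older) / (ln younger − ln older). For neutralising antibody, 2.0 mg, Week 6: ln(150.6/135.7) / ln(159.9/135.7) = 0.104/0.164 = 0.635. The eight reported pooled titres give weights of 0.62 to 0.65, close to the planned 240/400 = 0.60. The by-age titres are therefore consistent with the pooled ones, and the reading was made.

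The ELISpot figures do not reconcile in the same way. For 1.0 mg at Week 6 the all-ages median is 6.7, below both age-group medians (7.6 and 10), which cannot happen if the two groups make up the whole.

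**3. What the reported figures imply.** The ratios below are 2.0 mg over 1.0 mg geometric mean fold-rises. Section 1.3.7 gives the components but neither the ratios nor any interval.

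| Assay | All ages | 18-50 | 51 and over |
|---|---|---|---|
| Neutralising (Phase 2 primary) | 4.3/2.9 = 1.48 | 5.0/3.3 = 1.52 | 3.2/2.3 = 1.39 |
| Binding (not a Phase 2 primary endpoint) | 23.5/7.8 = 3.01 | 26.5/7.9 = 3.35 | 19.2/7.6 = 2.53 |

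The ratio is above 1 in both age groups for both assays.

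**4. Could these figures show an age difference?** With 3:3:1:1 allocation the planned number per active arm is 240 × 3/8 = 90 at 18-50 and 160 × 3/8 = 60 at 51 and over. The protocol gives no SD, so assume 1.0 for the ln fold-rise. The 95% factor for the ratio of ratios is exp(1.96 × √(2/90 + 2/60)) = 1.59. The reported ratios of ratios are 1.52/1.39 = 1.09 (neutralising) and 3.35/2.53 = 1.33 (binding). Both lie inside that factor, so no age-by-dose difference is demonstrated.

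**5. Is a by-age contrast precise enough to be worth printing?** The CI factor for the 2.0 versus 1.0 mg ratio is exp(1.96 × SD × √(2/n)). At SD 1.0:

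- pooled, n = 150 per arm: 1.25
- 18-50, n = 90: 1.34
- 51 and over, n = 60: 1.43

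Using t quantiles, as 8.5.1 specifies, moves these by at most 0.01. Over an assumed SD of 0.8 to 1.5 the t-based ranges are 1.20-1.41 pooled, 1.27-1.55 at 18-50 and 1.34-1.72 at 51 and over. For 65 and over alone (40 × 3/8 = 15 per arm) the range is 1.82-3.07, which is why a two-band split is the workable one.

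For Phase 3, 102 per age group at 2:1 is about 68 and 34. At SD 1.0 the active-versus-placebo factor is exp(1.96 × √(1/68 + 1/34)) = 1.51 per age group, against exp(1.96 × √(1/136 + 1/68)) = 1.34 pooled. Per-protocol exclusions and the existing strata would widen both.

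**The case against.** The other side has real weight.

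- **The by-age data were read and used.** Sections 1.3.7.1 to 1.3.7.3 give binding, neutralising and ELISpot results by dose and age group, and Section 1.3.6 records that 2.0 mg was advanced. A reader might infer that immunogenicity is never analysed by age. Section 1.3.7 contradicts that.
- **The formal Phase 2 objective does not mention age.** Table 6 asks only to "Evaluate the cellular and humoral immune response to INO-4800", and Section 8.3 calls Phase 2 an estimation segment without hypotheses. A reader might infer that the planned analysis cannot answer the Phase 2 objective. That is too strong: the Table 6 objective is not age-specific, and the dose decision already had by-age data.
- **Persistence by age has no Phase 2 objective behind it.** Antibody persistence is a Phase 3 exploratory objective without an age element.
- **Pooling does not bias the Phase 3 contrast.** Randomisation is stratified by age, and the planned seronegative population is itself half and half (3357/3357 in Table 2), so the 102 + 102 subset matches the plan. A reader might infer that the age quota distorts the Phase 3 result. The documents cannot support or size that: 8.5.2.2 compares arms by ratios of fold-rises, and neither placebo fold-rises by age nor the achieved age mix is given.
- **Nothing forbids an age split, and later text may differ.** The wording appears in both country-specific versions shown (1.0USA and 2.0USA). The file also carries the tail of a version 7.0 whose statistical section is not visible.

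What survives is narrower. The reading in 1.3.7 covers Week 6 only, gives no contrast or interval, and uses a cut at 51 that the Phase 2 analysis plan does not name and that merges two enrolment bands. Its safety comparison is by dose, not by age, although the same section says the by-age decision also rests on safety.

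**Conclusion.** The point holds as a pre-specification inconsistency. In the versions shown, Section 8.5 lists its immunogenicity strata and omits age, against Sections 3.0, 1.3.7 and 6.5. As a result no by-age contrast with a confidence interval is planned at Week 6, 30 or 56 in Phase 2, or anywhere in Phase 3.

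The demonstrated consequence is modest. The reported ratios are above 1 in both age groups, and the difference between age groups lies within sampling noise under the assumed SD. Nothing here implies a change to the dose choice or a bias in the Phase 3 between-arm comparison. The textual finding rests on no assumption. The precision figures rest on an assumed ln-scale SD of 1.0 (range 0.8 to 1.5) and on the planned numbers per arm; ELISpot precision cannot be sized from the document. It should be corrected, because the remedy is almost free and brings the analysis into line with the stated aim.

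**What to change.** Add age group (18-50, 51 and over) to the listed strata in Section 8.5.1 (Phase 2), Section 8.5.2.2 and Section 8.5.9.2. In each age group report the between-arm ratio of fold-rises or difference in medians with its 95% CI, beside the pooled result. State that 51-64 and 65 and over are combined for precision.

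Because Section 1.3.7 makes safety part of the by-age decision, add the same split to the Phase 2 safety summaries in Section 8.5.3.1.

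The cost is wording and extra table columns, with no new data, visits or assays. The by-age intervals will be wider than the pooled one, by the factors shown in the working, and should be presented as estimates.

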8.5.2 SECONDARY ANALYSES

8.5.2.1 Efficacy

Phase 3 Segment

The secondary efficacy incidence endpoints will be analyzed in the same manner as the primary hypothesis, but with 95% CIs and without the hypothesis test p-value.

8.5.2.2 Immunogenicity

Phase 3 Segment

Post-baseline increases from baseline in interferon- γ ELISpot response magnitudes will be compared between treatment groups using differences in medians and associated non-parametric 95% CIs.

Post-baseline increases from baseline in neutralizing antibody response titers will be compared between treatment groups using ratios of geometric mean fold-rises and associated t-distribution based 95% CIs.

The summaries listed above will be stratified according to disease status of the subjects and by baseline SARS-CoV-2 serostatus.

Valid samples for statistical analysis purposes will be those collected: at least 6 and no more than 30 days after Dose 2 for the Week 6 timepoint; at least 174 and no more than 198 days after Dose 2 for the Week 30 timepoint; and at least 356 and no more than 380 days after Dose 2 for the Week 56 timepoint. Baseline is defined as the last measurement prior to the first treatment administration.

The PP population will be used for these immunogenicity analyses.

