Subjects 18-50 years old in the 1.0 mg dose group had a GMT that was 148.5 at Day 0 compared to 1182.1 at Week 6. The geometric mean fold rise in binding antibody titers was 7.9. The GMT for the 2.0 mg dose group was 99.5 at baseline compared to 2671.2 at Week 6. The geometric mean fold rise was 26.5.

Subjects \geq 51 years old in the 1.0 mg dose group had a GMT that was 87.5 at Day 0 compared to 623.3 at Week 6. The geometric mean fold rise in titers was 7.6. The GMT for the 2.0 mg dose group was 84.0 at baseline compared to 1613.7 at Week 6. The geometric mean fold rise in binding antibodies was 19.2.

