1.3.7.2 Neutralizing Antibody Response

The neutralizing antibody response was measured for all Phase 2 subjects at Days 0 and Week 6. Across all ages the geometric mean titer (GMT) for the 1.0 mg dose group was 32.2 at Day 0 compared to 93.6 at Week 6. The geometric mean fold rise in neutralizing titers was 2.9. The GMT for the 2.0 mg dose group was 35.8 at baseline compared to 150.6 at Week 6. The geometric mean fold rise was 4.3.

INO-4800	COVID19-311
Inovio Pharmaceuticals, Inc.	Clinical Protocol

Subjects 18-50 years old in the 1.0 mg dose group had a GMT that was 34.5 at Day 0 compared to 112.6 at Week 6. The geometric mean fold rise in neutralizing titers was 3.3. The GMT for the 2.0 mg dose group was 32.2 at baseline compared to 159.9 at week 6. The geometric mean fold rise was 5.0.

Subjects \geq 51 years old in the 1.0 mg dose group had a GMT that was 28.4 at Day 0 compared to 67.4 at Week 6. The geometric mean fold rise in neutralizing titers was 2.3. The GMT for the 2.0 mg dose group was 43.3 at baseline compared to 135.7 at Week 6. The geometric mean fold rise was 3.2.

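### Phase 3 antibody comparisons fix the log-baseline slope at 1 and leave out the age stratum; ANCOVA on log titre would be a cheap improvement, not a repair of an invalid analysis

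*Protocol*

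**What the plan says.** Section 8.5.2.2 fixes the Phase 3 secondary analysis of neutralising antibody: "titers will be compared between treatment groups using ratios of geometric mean fold-rises and associated t-distribution based 95% CIs". It adds that "The summaries listed above will be stratified according to disease status of the subjects and by baseline SARS-CoV-2 serostatus". Section 8.5.9.2 uses the same method for Phase 3 ELISA titres and repeats it for neutralising titres, stratified by disease status only. Section 8.5.1 sets it for the Phase 2 primary antibody endpoint, where groups are "compared between treatment groups using ratios of geometric mean fold-rises and associated t-distribution based 95% CIs". None of these sections names a baseline or age covariate.

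Section 8.1 states that the formal SAP is made up of the sections that follow it, so the method is fixed here and not deferred. Under Section 8.3, Phase 2 is estimation only, and Phase 3 has no formal hypothesis besides primary efficacy. Section 6.5 takes the planned immunogenicity set from the first 102 subjects in each of two age groups at the sites collecting cellular samples, plus subjects with COVID-19. Section 8.7 randomises 2:1, stratified by age (18-50, 51 and over) and by underlying conditions.

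**The concern.** A ratio of fold-rises is a change-score analysis on log titre: the whole of the log baseline is subtracted. That is efficient only if the post-dose log titre rises one-for-one with the baseline log titre. With a flatter relationship, two things follow. An arm that happens to start higher is marked down too far, and baseline variability is added to the comparison without a matching gain. Age is a randomisation factor and is related to response: at 2.0 mg the Phase 2 Week 6 binding GMT was 2671.2 at 18-50 and 1613.7 at 51 and over. The planned comparison leaves that variation in the error term.

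At stake are the stability and width of the vaccine-versus-placebo titre ratios in Phase 3. For an estimation endpoint, those are the whole product. No efficacy conclusion or error rate is affected.

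**Working it through.** **Inputs.** Phase 2 GMTs and geometric mean fold-rises from Section 1.3.7; subset size from Section 6.5; allocation from Section 8.7. The protocol gives no SD, no baseline-to-post correlation or slope, no placebo titre and no Phase 3 baseline titre.

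**Reproducing the plan's figures.** Fold-rise = Week 6 GMT / Day 0 GMT. For neutralising titres at age 51 and over:
- 1.0 mg: the group "had a GMT that was 28.4 at Day 0 compared to 67.4 at Week 6", and 67.4/28.4 = 2.37. Stated: "The geometric mean fold rise in neutralizing titers was 2.3".
- 2.0 mg: "The GMT for the 2.0 mg dose group was 43.3 at baseline compared to 135.7 at Week 6", and 135.7/43.3 = 3.13. Stated: "The geometric mean fold rise was 3.2".

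Of the 12 stated fold-rises, 10 reproduce within 3%. The other two differ by 3.2% and 6.3%, which could arise if fold-rises use only paired samples.

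**Fold-rise ratio against Week 6 ratio, 2.0 mg versus 1.0 mg.**

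| Titre, age | Day 0 GMT ratio | Week 6 GMT ratio | Ratio of stated fold-rises |
|---|---|---|---|
| Neutralising, all | 35.8/32.2 = 1.11 | 150.6/93.6 = 1.61 | 4.3/2.9 = 1.48 |
| Neutralising, 18-50 | 32.2/34.5 = 0.93 | 159.9/112.6 = 1.42 | 5.0/3.3 = 1.52 |
| Neutralising, 51+ | 43.3/28.4 = 1.52 | 135.7/67.4 = 2.01 | 3.2/2.3 = 1.39 |
| Binding, all | 93.5/123.3 = 0.76 | 2210.0/938.8 = 2.35 | 23.5/7.8 = 3.01 |
| Binding, 18-50 | 99.5/148.5 = 0.67 | 2671.2/1182.1 = 2.26 | 26.5/7.9 = 3.35 |
| Binding, 51+ | 84.0/87.5 = 0.96 | 1613.7/623.3 = 2.59 | 19.2/7.6 = 2.53 |

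The two largest gaps run in opposite directions. In the binding 18-50 row it was the 1.0 mg group that started higher: it "had a GMT that was 148.5 at Day 0 compared to 1182.1 at Week 6".

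**What ANCOVA would change.** With common within-group slope b on log titre, the estimated ratio is (Week 6 ratio) / (baseline ratio)^b. Setting b = 1 gives the fold-rise ratio and b = 0 the Week 6 ratio. The shift from fold-rise to ANCOVA is therefore (baseline ratio)^(1-b). From the GMTs, over an assumed range of b:

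| Slope b | 1 | 0.75 | 0.5 | 0.25 | 0 |
|---|---|---|---|---|---|
| Neutralising 51+, ratio | 1.32 | 1.47 | 1.63 | 1.81 | 2.01 |
| Shift from fold-rise | 1.00 | 1.11 | 1.23 | 1.37 | 1.52 |
| Binding 18-50, ratio | 3.37 | 3.05 | 2.76 | 2.50 | 2.26 |

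For neutralising titres at all ages the largest shift is 1.11-fold.

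**Precision.** Let s0 and s1 be the baseline and post-dose log SDs and r their correlation. The change-score variance is proportional to s0² + s1² - 2·r·s0·s1, the ANCOVA variance to s1²(1 - r²).
- s0 = s1: the variance ratio is 2/(1 + r). At r = 0 it is 2.00 (intervals 41% wider); at r = 0.5 it is 1.33 (15% wider).
- s0 = s1/2: the variance ratio is (1.25 - r)/(1 - r²). At r = 0 it is 1.25 (12% wider); at r = 0.5 it is 0.75/0.75 = 1.00 (no loss).

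**Chance baseline imbalance in Phase 3.** 2 × 102 = 204 subjects at 2:1 is about 136:68 overall and 68:34 per age group. The 95% limit of the baseline ratio is 10^(1.96·SD·√(1/n1 + 1/n2)). For an assumed log10 SD of 0.2 to 0.6 this is 1.14 to 1.50-fold overall and 1.21 to 1.77-fold within one age group. The log of the imbalance is then multiplied by (1 - b) to give the shift.

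**The case against.** The strongest reply is that the planned method is valid and nothing turns on the choice. A fold-rise is already adjusted for baseline, and Section 8.5.2.2 also stratifies by serostatus. Over randomisation the ratio is unbiased, and the t-based interval already carries chance baseline variation. All six Phase 2 comparisons favour 2.0 mg on either measure, and that dose has been chosen. All of this stands, and it limits the point to conditional bias and lost precision.

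A reader might infer three stronger things that the documents do not support.
- That the plan's ratio is wrong by 1.5-fold. That figure is the gap to a Week 6-only comparison and equals the ANCOVA shift only at slope 0. It comes from the two worst of six dose-versus-dose comparisons in Phase 2 age subgroups, not from vaccine versus placebo in Phase 3.
- That baseline handling matters more than sampling error. No SD or interval is reported, so the two cannot be compared.
- That intervals are 15-41% too wide. That range needs equal baseline and post-dose variances; under another plausible assumption the loss is 12% or nil.

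Nor can baseline titres be dismissed as assay noise. The protocol does not show it, and Phase 3 also plans about 402 seropositive subjects. ANCOVA has its own weakness: a single slope may fit poorly when placebo titres track baseline and vaccinees' do not, or when many values sit near the assay floor.

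Finally, the statistical text relied on is in versions 1.0USA and 2.0USA. The corresponding sections of version 7.0 are not in the available text.

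**Conclusion.** The point holds as an efficiency and stability improvement to the Phase 3 antibody comparisons. Sections 8.5.2.2 and 8.5.9.2 fix the log-baseline slope at 1 and leave out the age stratum, although Day 0 titres and age are both available. ANCOVA with an estimated slope is, in large samples, never less precise, and it removes the conditional bias from a chance baseline difference.

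The size is not known. For a baseline imbalance like the largest in Phase 2 (1.52-fold), the ratio would move by about 1.5-fold at slope 0, 1.23-fold at slope 0.5 and not at all at slope 1. Intervals would be from 0 to about 41% wider than necessary over the variance ratios and correlations considered. Slope, SD and correlation are all assumptions here. Because these endpoints carry no hypothesis, alpha or power, priority is low to moderate.

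**What to change.** For the Phase 3 neutralising and ELISA titres in Sections 8.5.2.2 and 8.5.9.2, compare arms by ANCOVA on log titre with terms for arm, log Day 0 titre and age stratum (18-50, 51 and over), within the serostatus strata already planned. Report the adjusted geometric mean ratio with its 95% CI, and keep the fold-rises as descriptive summaries.

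For the remaining Phase 2 timepoints, use the same model only as a labelled supplementary analysis. Group-level Week 6 results by dose are already reported in Section 1.3.7, so replacing the Phase 2 primary method now would be a post hoc change.

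The cost is a few degrees of freedom, a common log-linear slope assumption that should be checked against values near the assay floor, and a wording amendment to the protocol, since the formal SAP sits there. No new data are needed: Table 4 already schedules the Day 0 humoral sample.
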